**Criteria for Evaluation:**

A large number of intraoperative and postoperative clinical variables that include cerebral oximetry, pulse oximetry, blood pressure, a composite outcome measure and clinical variables representing organ function will be assessed with the primary endpoint being the determination of which clinical variables are improved, if any, as a result of being randomized to open NIRS data monitoring with a predefined desaturation intervention algorithm guideline. The Mini Mental Status exam and Confusion Assessment Method test will be used to determine if any measured clinical variables have an effect upon neuropsychological outcomes. The frequency and effectiveness of the various cerebral desaturation mitigating interventions will be assessed in the intervention cohort.

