### **6.2 Primary Objective**

The primary objective of this pilot study is to identify the most relevant clinical outcome variables which significantly diverge as a result of being randomized to the intervention cohort vs. the control cohort so that a larger, multicenter, prospective, randomized controlled clinical trial can be designed to further test the primary hypothesis as stated in the preceding section. The subsequent larger, multicenter trial will be conducted to definitively demonstrate the ability of INVOS® 5100 guided NIRS-based bi-frontal monitoring to improve clinical outcomes in this surgical patient group and potentially establish a new U.S. Food and Drug Administration cleared indication for this monitoring modality.

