### **6.3 Secondary Objectives**

Secondary objectives of this pilot study include the following:

- 1) Assess the frequency of cerebral desaturations in both the intervention and control cohorts by examining both the total number of patients experiencing any cerebral desaturation as well as the total number of events among patients experiencing any cerebral desaturation (of at least 5% below baseline and progressively larger desaturations). These analyses will be conducted on the entire study population as well as upon each cohort. The Area Under the Curve (AUC) analysis

technique [incremental desaturation categories will be assessed based upon 5 to 50% decreases, measured in 5% increments, from established room air baseline as well as oxygen supplemented pre-incision baselines as well as desaturations below absolute measured rSO2 values] will be employed to conduct these analyses.

- 2) Assess the frequency of adverse clinical events and serious adverse events overall and in each cohort.
- 3) Perform a comprehensive assessment of the frequency and efficacy of predefined rSO2 desaturation mitigation interventions and their collective ability to affect the observed cerebral oximetry values.
- 4) Assess the interventional cohort's preoperative demographics and collected covariates for association with the ease or difficulty of mitigating observed cerebral desaturation events.

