#### **6.4 Exploratory Objectives**

Exploratory objectives will include performing all possible comparisons of the two groups based upon all collected perioperative variables to examine the potentially significant relationships between the collected clinical variables representing surrogates of organ perfusion/function and cerebral oximetry desaturations (AUCrSO2). The following exploratory endpoints will be assessed:

- Logistic regression analysis to determine the most relevant AUCrSO2 desaturation value(s) associated with any detrimental clinical outcome(s) monitored in this study
- Logistic regression analysis to determine the most relevant AUC blood pressure values associated with any detrimental clinical outcome(s) monitored in this study
- Comparison of baseline rSO2 values (room air and oxygen supplemented) to all collected clinical variables to assess for possibly significant associations

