## **Schematic Diagram of Trial Design**

## 7.4 Study Variables

### 7.4.1 Primary Endpoints

The relationship between the observed cerebral oximetry data and a number of predefined intraoperative and postoperative clinical variables will serve as the primary endpoints of this trial. The clinical variables will include the following intraoperative and postoperative (PACU or initial 12 hours of the ICU stay) parameters:

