#### 7.4.1.1 Intraoperative:

- Area under the curve of cumulative rSO2 desaturations (AUCrSO2) of progressive categorical degrees that will include the following:
  - < 5% of established room air baseline and oxygen supplemented baseline ○ < 10% of established room air baseline and oxygen supplemented baseline ○ < 15% of established room air baseline and oxygen supplemented baseline ○ < 20% of established room air baseline and oxygen supplemented baseline ○ < 25% of established room air baseline and oxygen supplemented baseline ○ < 30% of established room air baseline and oxygen supplemented baseline ○ < 35% of established room air baseline and oxygen supplemented baseline ○ < 40% of established room air baseline and oxygen supplemented baseline ○ < 60% of absolute measured value (if baseline > 60%) ○ < 55% of absolute measured value (if baseline > 55%) ○ < 50% of absolute measured value (if baseline > 50%) ○ < 45% of absolute measured value (if baseline > 45%) ○ < 40% of absolute measured value ○ < 35% of absolute measured value

○ < 30% of absolute measured value ○ < 25% of absolute

measured value ○ < 20% of absolute measured value

- Area under the curve for cumulative, high and low intraoperative values outside of preestablished, individualized patient blood pressure goals based upon preoperatively observed blood pressure values as well as values clinically accepted to provide adequate organ perfusion. This analysis will be performed for systolic, diastolic and mean arterial pressures (AUCSBP-hi, AUCSBP-low, AUCSBP-cum, AUCDBP-hi, AUCDBP-low, AUCDBP-cum, AUCMAP-hi, AUCMAP-low, AUCMAP-cum). All intraoperative pressure data will be collected with either invasive arterial catheterization [Q30 secs] or non-invasive blood pressure monitoring [Q3 min] as determined by the attending anesthesiologist caring for the subject.
- Area under the curve of intraoperative progressive categorical pulse oximetry (SpO2) desaturations (AUCSpO2) including the following:
  - AUCSpO2 < 95% regardless of intraoperative FiO2 values ○
  - AUCSpO2 < 90% regardless of intraoperative FiO2 values ○
  - AUCSpO2 < 85% regardless of intraoperative FiO2 values ○

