### 11.3 Protocol Assessments and Procedures – Intraoperative and Immediate Postoperative Period

#### 11.3.1 General Intraoperative and Immediate Postoperative Period Description

During this period a host of clinical variables will be collected on each subject that will serve as the primary endpoints of this pilot study.

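### Section 7.4.1 makes an oximetry-outcome association primary, against the between-arm question set elsewhere, and section 15 plans no between-arm estimate or interval

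*Combined protocol and SAP*

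**What the plan says.** Four places describe what is primary.

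- Synopsis, Criteria for Evaluation: "the primary endpoint being the determination of which clinical variables are improved, if any, as a result of being randomized to open NIRS data". Open monitoring comes with the intervention guideline.
- Section 6.2, Primary Objective: "identify the most relevant clinical outcome variables which significantly diverge as a result of being randomized to the intervention cohort vs. the control cohort". The primary hypothesis (synopsis and section 6.1) likewise concerns benefit to the intervention cohort against the control cohort.
- Section 7.4.1 states a different target: "The relationship between the observed cerebral oximetry data and a number of predefined intraoperative and postoperative clinical variables will serve as the primary endpoints". The arms are not mentioned.
- Section 11.3.1: "During this period a host of clinical variables will be collected on each subject that will serve as the primary endpoints of this pilot study". This is compatible with the synopsis but ranks nothing.

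The list under 7.4.1 opens, in 7.4.1.1, with areas under the curve for rSO2 desaturation "of progressive categorical degrees that will include the following". The first secondary objective in section 6.3 already covers that ground: "Assess the frequency of cerebral desaturations in both the intervention and control cohorts".

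Section 6.4 lists as exploratory the logistic regressions that look for rSO2 AUC values "associated with any detrimental clinical outcome(s) monitored in this study". It also places there "all possible comparisons of the two groups based upon all collected perioperative variables to examine the potentially significant relationships between the collected clinical variables" and cerebral desaturations. The synopsis carries the same exploratory list.

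Section 15 (repeated in the synopsis) plans t-tests for preoperative variables, a Wilcoxon rank-sum test for clinical data between groups, and forward stepwise logistic regression relating desaturations to clinical variables at p<0.05. It mentions no effect measure and no confidence interval. Section 5.4 says the pilot is to define the endpoints and statistical design for establishing benefit.

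**The concern.** The two descriptions of the primary endpoint are different estimands. A comparison of outcomes between randomised arms estimates the effect of open monitoring with its algorithm. A relationship between observed rSO2 and outcomes does not. rSO2 is measured after randomisation, and the algorithm, used only in the intervention group (Table 1), exists to change it. Sicker patients may both desaturate more and do worse, so an association could appear with no benefit from monitoring.

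If 7.4.1 were followed as written, the headline result could not answer the hypothesis in 6.1. The analysis that could answer it might be reported as exploratory, because 6.4 places all two-group comparisons there.

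The second issue is what the pilot hands on. Planning the next trial needs effect sizes, event rates and their precision. Rank-sum p values supply none of these, and section 6.2 makes significance a criterion for carrying a variable forward.

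**Working it through.** **1. No figure to reproduce.** The sample size of 100 is given without power, effect size, SD or event rate. The contradiction is therefore checked on the text.

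**2. The sections side by side.**

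| Place | What is compared | Status given |
|---|---|---|
| Synopsis, Criteria for Evaluation | Outcomes by randomised arm | Primary endpoint |
| 6.1 and 6.2 | Outcomes by randomised arm | Primary hypothesis and objective |
| 7.4.1 | Oximetry data against clinical variables | Primary endpoints |
| 6.4, regression items | Outcomes against rSO2 AUC | Exploratory |
| 6.4, opening sentence | The two groups on all variables | Exploratory |
| 6.3, item 1 | Desaturation, overall and by cohort | Secondary |

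The association is thus primary in 7.4.1 and exploratory in 6.4. The arm comparison is primary in the synopsis and, on one reading, exploratory in 6.4. Because the 7.4.1 list includes the rSO2 AUCs, part of that endpoint relates oximetry to oximetry.

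**3. What section 15 would leave unreported.** Inputs: 50 per arm (100 randomised 1:1, no dropout assumed).

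- Standard error of a mean difference in SD units: √(2/50) = 0.20. The 95% half-width is 1.96 × 0.20 = 0.39 SD.
- Risk difference at an assumed 30% rate in both arms: 1.96 × √(2 × 0.3 × 0.7/50) = 0.18, or 18 percentage points.

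**4. Multiplicity, for illustration only.** Section 7.4.1.2 has 28 items besides the rSO2, blood pressure and SpO2 AUCs. Leaving out epidural use gives 27.

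- Expected false positives with no true effect: 27 × 0.05 = 1.35. This does not depend on correlation.
- Chance of at least one, if independent: 1 − 0.95^27 = 0.75.
- With equally correlated normal test statistics: 0.63 at an assumed correlation of 0.3, and 0.48 at 0.5.
- The denominator is a choice. Adding 16 intraoperative non-AUC items gives 44 and an expected 44 × 0.05 = 2.2. Counting every AUC as well gives about 124 and 6.2.

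**5. Selection on significance.** With standard error 0.20 and selection of favourable estimates at two-sided p<0.05, the mean selected estimate is 0.50 for an assumed true d of 0.2, 0.52 for 0.3 and 0.60 for 0.5. These overstate the truth by about 2.5, 1.7 and 1.2 times.

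**6. Would choosing the largest estimate avoid this?** Suppose all 27 outcomes have a true d of 0.2 and the largest estimate is chosen. The expected maximum of 27 independent standard normals is about 2.0, so the overstatement is 1 + 2.0 × √(1 − ρ) × (0.20/0.20). That is about 3.0 times if independent, 2.7 at ρ = 0.3 and 2.4 at ρ = 0.5. Estimates and intervals show the imprecision, but they do not remove selection bias.

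**The case against.** The strongest reply is that the intent is clear. The hypothesis, the objective and the synopsis endpoint all concern the arms, section 11.3.1 fits them, and section 15 puts the between-group test before the regression. On this view one sentence in 7.4.1 is out of line and 6.4 is loosely worded. Much of this stands. A reader might infer that the primary question cannot be determined at all, but the documents do not support that. Section 6.2 also states an objective, not an endpoint; of the sections set out here, only the synopsis attaches the words primary endpoint to the arm comparison. What remains is that the section headed Primary Endpoints says something else, and an analyst following it would produce a different result.

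A reader might also infer that no between-arm analysis is planned. The rank-sum test is one; what is missing is an estimate and an interval.

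A third reply is that a pilot meant to find endpoints may leave its list open. That is fair. It is why naming a lead outcome in advance is optional here, and why a multiplicity adjustment need not be a gate. It does not excuse two definitions of primary, and it strengthens the case for estimates.

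Finally, the multiplicity figures do not measure the contradiction and would be unchanged if 7.4.1 were corrected. The 75% figure assumes independence, yet stroke, myocardial ischemia and red-cell transfusion each appear twice in the list, and the composite contains several other listed items. This objection stands, so those figures are kept as illustration.

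**Conclusion.** The concern holds in two parts. First, section 7.4.1 contradicts the synopsis endpoint, the primary hypothesis, the 6.2 objective and the exploratory status given in 6.4. This rests on the text and needs no assumption. Followed literally, it would make a non-randomised association the primary result. Second, section 15 plans no between-arm estimate or interval, which leaves the pilot short of its stated purpose. With 50 per arm and no dropout, each comparison carries an uncertainty of about ±0.39 SD, or ±18 points at an assumed 30% rate, which the planned output would not show.

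It would be wrong to read the 75% figure as the chance that this trial ends in a false claim. It depends on 27 chosen items, independence and no true effect, and falls to about 48-63% at assumed correlations of 0.5-0.3. A chance finding would also be retested in the planned larger trial, so the cost is a poorly chosen endpoint or an optimistic design there. The vasoactive-drug component of the composite raises a separate question and is not part of this point.

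The change should be made, but the defect does not undermine the data to be collected.

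**What to change.** 1. Reword 7.4.1 so that the primary analysis is the between-arm comparison of the listed clinical outcomes, in line with 6.2 and the synopsis. State whether the monitoring AUCs belong to that list, given that 6.3 already covers rSO2 desaturation by cohort. Label oximetry-outcome associations exploratory, and say in 6.4 that the primary between-arm comparisons are not.
2. In section 15, report each listed outcome as a between-arm estimate with a 95% confidence interval: for example, a Hodges-Lehmann difference beside the rank-sum test and a risk difference for yes/no items. Give the number evaluable for each outcome and the number of comparisons made.
3. Do not select the next trial's endpoint on p<0.05 alone. Weigh estimates, intervals, event rates and clinical relevance, and state that any estimate picked from many is likely to be too large. Naming one lead outcome in advance is optional.

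The cost is protocol and SAP wording and some extra analysis, with no new data. Fewer results will be presented as findings.

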## 8.5 Device Image

## 8.6 Device Modification

The subjects randomized to the control group will be monitored with a modified device following the acquisition of the baseline NIRS data. The modification involves electronic blinding of the data via an adjustment made to the device by the manufacturer that prevents the active display of the current data and graphic trends on the display console. However, the modified device will still electronically store the acquired NIRS data for later analysis. The use of this modified version of the device will help to reduce investigator bias that might be introduced if a blinder were affixed to the display console.

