## **11 PROTOCOL ASSESSMENTS AND PROCEDURES**

The Schedule of Assessments which details the sequence of assessments and procedures is presented in Table 1. Note that as described in Section 7.2 there are four separate periods that this study is divided into that include the following: screening, baseline, intraoperative and immediate postoperative and postoperative follow up.

Table 1: Schedule of Assessments

	Screening	Baseline Acquisition	Intraoperative and Immediate Postoperative	Postoperative Follow Up
Study Assessment				
Review of inclusion/exclusion criteria	X			
Informed consent	X			
Demographics	X			
Medical history	X			
Randomization		X		
MMSE & CAM testing		X		X
Serum creatinine	X			X
Obtain baseline room air and O 2 supplemented rSO 2		X		
Continuous rSO 2 , SpO 2 , blood pressure data collection			X	
Employ rSO 2 desaturation algorithm (intervention group only)			X	
Continuous intra/immediate post-operative clinical variable collection			X	
PACU and ICU clinical variable collection			X	
Postoperative clinical variable collection			X	X
Adverse and Serious Adverse Event Monitoring		X	X	X
Telephone interview				X

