#### 11.3.2 Serial rSO2, SpO2 and Blood Pressure Data Collection

Anesthesia induction will be accompanied by continuous electronic acquisition of the rSO2, SpO2 and MAP data. PICIS will be used to collect blood pressure data as well as rSO2 data in individuals randomized to the intervention group. The INVOS devices will also be collecting the rSO2 data in both groups of subjects for download at a later time. Note that the time on the oximeter will be synchronized with the time on the PICIS Anesthesia Computer prior to the collection of any NIRS or hemodynamic data.

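### Effectiveness of the desaturation interventions is to be assessed in the open arm, with no control comparator for recovery after an event

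*Combined protocol and SAP*

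**What the plan says.** Under Criteria for Evaluation, the synopsis states: "The frequency and effectiveness of the various cerebral desaturation mitigating interventions will be assessed in the intervention cohort". Secondary objective 3 (synopsis and Section 6.3) covers how often the predefined interventions are used, how efficacious they are, and "their collective ability to affect the observed cerebral oximetry values". It names no cohort, comparator, recovery criterion or time window. Objective 4 is explicitly confined to the open arm: "Assess the interventional cohort's preoperative demographics and collected covariates for association with the ease or difficulty of mitigating observed cerebral desaturation events". Section 15 gives a t-test for preoperative variables, a rank-sum test between groups for the observed clinical data, and a stepwise logistic regression. None is assigned to objective 3.

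A comparator exists in the data. For the blinded arm, Section 8.6 says that "the modified device will still electronically store the acquired NIRS data for later analysis". Section 11.3.2 has the oximeters collecting rSO2 "data in both groups of subjects for download at a later time", with the oximeter clock synchronised to the anesthesia computer. Both arms have both baselines recorded (Sections 7.2.2, 10.2 and 10.3), and Table 1 restricts the algorithm to the intervention group.

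Some oximetry analysis by cohort is planned. Objective 1 covers patients with desaturation and event counts in each cohort, using AUC. Sections 7.4.1.1 and 7.4.1.2 list AUC below a series of cuts against both baselines. Section 6.4 adds all possible comparisons of the two groups.

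**The concern.** Efficacy and ability to affect rSO2 are causal terms. Action begins when rSO2 has just fallen below a threshold, that is, at a point selected for being low. A fluctuating signal picked at a low point tends to rise again without help. A transient cause may also pass, or be dealt with by usual care for blood pressure and SpO2. The share of events that resolve after action in the open arm therefore combines three things: the effect of the algorithm, spontaneous recovery, and recovery under usual care. One arm alone cannot divide them.

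The stake is the next trial. This pilot exists to guide the design of a larger multicenter study (Sections 5.4 and 6.2). An uncontrolled success rate for the algorithm, carried into that design, could make the algorithm look stronger than it is. The blinded arm records the same kind of events without rSO2-guided action, and no planned analysis uses them for this purpose.

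**Working it through.** The plan states no figure for this objective and no power calculation, so there is nothing to reproduce. The only numerical input from the documents is 100 subjects randomised 1:1, which is 50 per arm. All rates and trace parameters below are assumptions.

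**1. What a one-arm figure measures.** Let *s* be the recovery proportion without the algorithm and *d* the algorithm's effect. The open-arm figure is *s + d*; the between-arm difference is (*s + d*) − *s* = *d*.

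| Recovery without algorithm | Algorithm effect | Open arm reads | Between-arm difference |
|---|---|---|---|
| 30% | 0 | 30% | 0 |
| 50% | 0 | 50% | 0 |
| 70% | 0 | 70% | 0 |
| 50% | 20 points | 70% | 20 points |

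An open-arm reading of 70% fits both an inert algorithm (row 3) and a useful one (row 4).

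**2. How large *s* might be.** I simulated traces with no treatment effect: mean 8% to 12% below baseline, SD 7%, time scale 5 to 40 minutes, one sample every 30 seconds. An event is a downward crossing of −20%. Recovery is any sample back above the threshold within 5 minutes.

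- Jagged trace (Ornstein-Uhlenbeck): 79% to 97% recover. If the drop must first last 2 minutes, 56% to 94%.
- Smooth Gaussian trace with the same mean, SD and nominal time scale: about 1% to 48% recover.

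The direction is constant, because *s* can only add to the open-arm figure. The size depends mainly on which process is assumed, and the documents hold no rSO2 data that would choose between them.

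**3. What the planned AUC comparison covers.** AUC combines depth and duration, so faster recovery lowers it. If open monitoring plus algorithm did nothing, the expected AUC would be equal in the two randomised arms. This comparison therefore bears on collective efficacy. It covers prevention and treatment of desaturation together, and it does not isolate recovery after an event. The listed cuts include 10% and 20% against both baselines, so the AUC for either stated trigger is already among the endpoints.

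**4. Precision of an event-level comparison.** Take one event per subject and recovery near 50%. The 95% half-width is 1.96 × √(2 × 0.25 / n). Power is for 50% versus 80% recovery, two-sided 5%: Φ[(0.30 − 1.96·se₀)/se₁], with se₀ = √(0.65 × 0.35 × 2/n) and se₁ = √((0.25 + 0.16)/n).

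| Share of 50 with an event | n per arm | Half-width | Power |
|---|---|---|---|
| 20% | 10 | 44 points | 28% |
| 40% | 20 | 31 points | 51% |
| 60% | 30 | 25 points | 69% |
| 80% | 40 | 22 points | 82% |

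For n = 20: 1.96 × √0.025 = 0.310; se₀ = 0.151, se₁ = 0.143, power = Φ(0.03) = 0.51.

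**5. Whether the same trigger can be applied to controls.** Sections 7.1 and 10.3 act on a fall of more than 20% from the oxygen-supplemented baseline, and Section 10.1 says more than 20% without naming the baseline. Section 7.2.3 defines a significant desaturation as at least 10% from the room air baseline. Until these are reconciled, a matching control event is not defined.

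**The case against.** The strongest reply is that the plan never states a before-and-after analysis. Efficacy is undefined, objective 3 names no cohort, and the limit to the open arm comes from one synopsis sentence. The algorithm's steps occur only in that arm, so their frequency and step-by-step results can only be described there. This stands in part. It rules out saying that natural recovery will be credited to treatment; that follows only if efficacy is read as recovery after action. But the synopsis sentence covers effectiveness as well as frequency, and nothing elsewhere supplies a comparator for it.

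A reader might also infer that the trial cannot tell an effective algorithm from natural recovery, or that an inert algorithm would be bound to look effective. The documents do not support either. Objective 1, the AUC endpoints and the between-group test allow a randomised comparison of desaturation burden. What is missing is the link from that comparison to objective 3, and any comparison of recovery after an event.

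Three further points stand and limit the remedy. Controls are not untreated; they receive usual care without rSO2 guidance, so their recovery is not purely spontaneous. Comparing events conditions on a crossing after randomisation, and open monitoring may prevent some crossings, so the events compared are not a randomised contrast. And in a pilot of this size the event-level result would be mainly descriptive.

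**Conclusion.** The point holds in a limited form. Followed as written, the synopsis gives an uncontrolled estimate for a named secondary objective phrased in causal terms, while a better comparison is available from data already collected. The primary objective is not affected.

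The direction of the bias is upward if efficacy is read as recovery after action. Its size is unknown: simulated recovery with no treatment effect runs from about 1% to 97% within 5 minutes. A reader who saw only the jagged-trace result might conclude that most recoveries, 79% or more, would happen anyway. That figure comes from the assumed process and should not be quoted as an estimate for this trial. The precision figures rest on assumed event shares of 20% to 80%, one event per subject and recovery near 50%.

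**What to change.** In the synopsis, Section 6.3 and Section 15:

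- Base any statement on the interventions' collective efficacy on the between-arm comparison of AUC below the trigger threshold in all randomised subjects.
- As support, apply the same trigger retrospectively to the stored control traces. Compare time to recovery, and AUC in the 10 minutes after crossing, with the clock starting at the crossing in both arms. Use the first event per subject; add all events, clustered by subject, as a sensitivity analysis.
- Define recovery in advance.
- State that the event-level comparison conditions on a post-randomisation event, that controls receive usual care, and that precision is low (half-width about 22 to 44 points for 40 down to 10 events per arm, on assumed rates).
- Label results for individual intervention steps as descriptive, since clinicians choose among the steps and may override the algorithm (Section 10.3).

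The trigger definitions in Sections 7.1, 10.1 and 10.3 and in Section 7.2.3 must be reconciled first; which of them applies is for the investigators to settle.

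The cost is added text in the statistical plan, that reconciliation, and extra programming, for an event-level result that will be mainly descriptive. No new data are needed.
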